3.6.2. Medical History

Medical history in addition to COVID-19 disease history and demographics will be collected at screening. Smoking status will be collected. Medication history of prescription or nonprescription drugs (including vaccinations), and dietary and herbal supplements taken within 30 days prior to the planned first dose will be collected.

3.6.3. Height and Weight

Height and weight will be measured and recorded at screening.

3.6.4. Laboratory Data

To determine if there are any clinically significant laboratory abnormalities, the hematological and clinical biochemistry and other safety tests will be assessed against the criteria specified in the Pfizer reporting standards. This assessment will take into account whether each participant's baseline test results are within or outside the laboratory reference range for particular laboratory parameter.

3.6.5. Vital Signs

Vital signs measure include temperature, pulse rate, respiratory rate, oxygen saturation level, and blood pressure.

4. ANALYSIS SETS (POPULATIONS FOR ANALYSIS)

Data for all participants will be assessed to determine if participants meet the criteria for inclusion in each analysis population prior to unblinding and releasing the database and classifications will be documented per standard operating procedures.

Population	Description
Full Analysis Set (FAS)	All participants randomly assigned to study intervention regardless of whether or not study intervention was administered.
Safety Analysis Set (SAS)	All participants who receive at least 1 dose of study intervention. Participants will be analyzed according to the intervention they actually received. A randomized but not treated participant will be excluded from the safety analyses.
Modified Intent-To-Treat (mITT)	All participants randomly assigned to study intervention, who take at least 1 dose of study intervention, who at baseline did not receive nor were expected to receive COVID-19 therapeutic mAb treatment and were treated ≤3 days of COVID-19 onset. Participants will be analyzed according to the study intervention to which they were randomized.
Modified Intent-To-Treat 1 (mITT1)	All participants randomly assigned to study intervention, who take at least 1 dose of study intervention, and who at baseline

Population	Description
	did not receive nor were expected to receive COVID-19 therapeutic mAb treatment. Participants will be analyzed according to the study intervention to which they were randomized.
Modified Intent-To-Treat 2 (mITT2)	All participants randomly assigned to study intervention, who take at least 1 dose of study intervention. Participants will be analyzed according to the study intervention to which they were randomized.
Per-Protocol (PP)	All participants in the mITT set without important protocol deviations considered to impact the interpretation of the primary efficacy endpoint. Protocol deviations will be reviewed to generate the list of participants with significant deviations to be excluded from the PP analysis set. The PP exclusion criteria will be finalized prior to breaking the blind.

For the primary efficacy analysis, the mITT set will be used and will be the primary analysis. A secondary analysis of the primary efficacy endpoint will be performed and will use mITT1 and mITT2 analysis set. For all other efficacy analyses mITT, mITT1, and mITT2 sets will be used (3 sets of analyses). The PP analysis set will be used in the analyses of primary efficacy endpoint. The Safety Analysis Set will be used in the analyses of the safety data.

For efficacy related analysis (mITT, mITT1 and mITT2), if a participant enters/is randomized into the study multiple times, a sensitivity analysis based on IA and PCD efficacy data will be conducted on the primary endpoint and all sensitivity analysis regarding primary endpoint. The data associated with first randomization will be included in the above sensitivity analyses conducted.

5. GENERAL METHODOLOGY AND CONVENTIONS

5.1. Hypotheses and Decision Rules

The primary hypothesis to be tested is whether or not there is a difference in proportion of participants with COVID-19 related hospitalization or death from any cause through Day 28 between PF-7321332/ ritonavir and placebo. The statistical hypothesis is as follows:

Ho:
$$\pi_{PF-7321332} - \pi_{placebo} = 0$$

versus
Ha: $\pi_{PF-7321332} - \pi_{placebo} \neq 0$ (1)

Where p PF-7321332 and p_{placebo} are the proportion of participants with hospitalization or death through Day 28. The hypotheses will be tested at an overall significant level of 5% (2-sided).

PFIZER CONFIDENTIAL
Page 18

Following the positive test of the primary endpoint, sequential testing will be performed for the following 2 secondary endpoints:

- Proportion of participants with COVID-19 related hospitalization or death from any cause through Day 28 who did not receive COVID-19 therapeutic mAb treatment, regardless of their onset of COVID-19 related signs and symptoms.
- Time (days) to sustained alleviation of all targeted signs/symptoms through Day 28.

The time to sustained alleviation of all targeted signs/symptoms through Day 28 will be tested first. If this test is positive, then will continue with second endpoint. The hypotheses will be tested at an overall level of 5% (2-sided).

Other secondary endpoints listed below will be subsequently tested following the Hochberg procedure¹:

- 1. Time (days) to sustained resolution of all targeted signs/symptoms through Day 28.
- 2. Proportion of participants with a resting peripheral oxygen saturation ≥95% at Days 1 and 5.
- 3. Number of COVID-19 related medical visits.

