## 9.1. Statistical Hypotheses

The primary hypothesis to be tested is whether or not there is a difference in proportion of participants with COVID-19 related hospitalization (as defined in Section 8.1.2) or death from any cause through Day 28 between PF-07321332/ritonavir and placebo. The statistical hypothesis is as follows:

Ho: 
$$\pi_{\text{PF-7321332}} - \pi_{\text{placebo}} = 0$$
  
versus  
Ha:  $\pi_{\text{PF-7321332}} - \pi_{\text{placebo}} \neq 0$  (1)

Where  $\pi_{PF-07321332}$  and  $\pi_{placebo}$  are the proportion of participants with hospitalization or death through Day 28.

Following the positive test of the primary endpoint, sequential testing will be performed for the following 2 secondary endpoints:

- 1. Proportion of participants with COVID-19 related hospitalization or death from any cause through Day 28 who did not receive COVID-19 therapeutic mAb treatment, regardless of their onset of COVID-19 related signs and symptoms.
- 2. Time (days) to sustained alleviation of all targeted signs/symptoms through Day 28.

Other secondary endpoints will be subsequently tested following the Hochberg procedure.

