### 9.3.3. Key Secondary Efficacy Endpoint(s)/Estimand(s) Analysis

# Proportion of participants with COVID-19 related hospitalization or death due to any cause through Day 28

The first key secondary efficacy endpoint is the proportion of participants with COVID-19 related hospitalization or death due to any cause through Day 28 in the mITT1 analysis set. The analysis for this endpoint is similar to the primary endpoint, but using the mITT1 analysis set.

# Time to sustained alleviation and time to sustained resolution of targeted COVID-19 sign/symptoms through Day 28

The key secondary endpoints of sustained alleviation and resolution will be defined for all targeted COVID-19 associated symptoms based on self-assessment.

Sustained alleviation of all targeted COVID-19 signs/symptoms is defined as the event occurring on the first of 4 consecutive days when all symptoms scored as moderate or severe at study entry are scored as mild or absent AND all symptoms scored mild or absent at study entry are scored as absent. The first day of the 4 consecutive-day period will be considered the First Event Date.

Sustained resolution is defined as when all targeted symptoms are scored as absent for 4 consecutive days. The first day of the 4 consecutive-day period will be considered the First Event Date.

For any symptoms not present at baseline, it must be absent at the last possible available day (prior to or at Day 25) to be counted as sustained alleviation/resolution. For symptoms with no reported severity in baseline, the symptom will have to be absent in order to consider alleviated/resolved (missing severity at baseline will be treated as mild).

Day 25 is the last possible day the symptom alleviation and resolution endpoints can be achieved (definition includes data from the subsequent three days) and Day 28 is the last day participants report their daily signs and symptoms.

The time to sustained symptom alleviation/resolution for the purpose of this study is defined as:

- For a participant with sustained symptom alleviation/resolution (event), time to event will be calculated as (First Event Date) (First Dose Date) +1.

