3.2. Secondary Endpoint(s)

- The first key secondary efficacy endpoint is the proportion of participants with COVID-19 related hospitalization or death due to any cause through Day 28 in the mITT1 analysis set.
- Incidence of treatment emergent adverse events (TEAEs).
- Incidence of SAEs and AEs leading to discontinuations.
- *Time (days) to sustained alleviation of all targeted signs/symptoms through Day 28.*
- Proportion of participants with severe signs/symptoms attributed to COVID-19 through Day 28.
- *Time (days) to sustained resolution of all targeted signs/symptoms through Day 28.*

- Duration of each targeted COVID-19 sign/symptom.
- Progression to a worsening status in 1 or more self reported COVID19 associated symptoms through Day 28.
- *Proportion of participants with a resting peripheral oxygen saturation* ≥95% *at Days 1 and 5.*
- Proportion of participants with death (all-cause) through Week 24.
- *PF-07321332 PK in plasma and whole blood (if feasible).*
- Viral titers measured via RT-PCR in nasal swabs over time.
- Number of COVID-19 related medical visits.
- Number of days in hospital and ICU stay in participants with COVID-19 related hospitalization.

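### SAP 5.1 puts the symptom test ahead of the mITT1 hospitalization/death test, reversing the protocol's fixed sequence

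*SAP*

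**What the plan says.** Protocol 9.1 states: "Following the positive test of the primary endpoint, sequential testing will be performed for the following 2 secondary endpoints". The numbered list that follows begins "1. Proportion of participants with COVID-19 related hospitalization or death from any cause through Day 28" (in participants without therapeutic mAb, regardless of onset, which is the mITT1 set) and continues "2. Time (days) to sustained alleviation of all targeted signs/symptoms through Day 28". Protocol 9.3.3 gives the same ranking: "The first key secondary efficacy endpoint is the proportion of participants with COVID-19 related hospitalization or death due to any cause through Day 28". The analysis set named there is mITT1.

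SAP 5.1 lists the same two endpoints in the same order, as unnumbered bullets. It then gives the only explicit gating rule in the section: "The time to sustained alleviation of all targeted signs/symptoms through Day 28 will be tested first". The next sentence reads: "If this test is positive, then will continue with second endpoint".

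Elsewhere the SAP keeps the protocol's ranking. SAP 3.2 opens its list with "The first key secondary efficacy endpoint is the proportion of participants with" hospitalization or death in mITT1. SAP Appendix 1 labels the mITT1 analysis as key secondary and the alleviation analysis as secondary.

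**The concern.** In a fixed sequence the order is the decision rule, because a non-significant result ends confirmatory testing for everything after it. If the primary test is positive, mITT1 is significant and alleviation is not, the protocol allows the mITT1 claim and SAP 5.1 forbids it. That claim carries the hospitalization/death result from participants treated within 3 days of onset to the full enrolled window of 5 days.

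Two orders on file also leave room to choose between them once results are known. The Amendment 4 summary says the objective of the 45% interim analysis was met, and Protocol 6.3.2 provides for a submissions team unblinded at group level. A late choice would therefore be hard to defend as independent of the data.

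**Working it through.** **1. The texts side by side**

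| Source | First | Second |
|---|---|---|
| Protocol 9.1, numbered list | mITT1 hospitalization/death | Alleviation |
| Protocol 9.3.3 | mITT1 (called first key secondary) | – |
| SAP 3.2 | mITT1 (called first key secondary) | – |
| SAP 5.1, bullets | mITT1 | Alleviation |
| SAP 5.1, gating sentences | Alleviation | The other endpoint, only if positive |

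Only the gating sentences differ. They also clash with the bullets above them: the second bullet is alleviation, so going on to the second endpoint after testing alleviation would, read literally, repeat the same test.

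**2. Inputs**

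Protocol 9.5 gives 7% versus 3.5%, 90% power, two-sided 5%, 1717 participants for the primary comparison, about 20% with mAb treatment, about 25% with onset more than 3 days before randomization, and 5% dropout. Allocation is 1:1. The documents give no power for the symptom test.

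**3. The plan's own figures**

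- Pooled two-proportion formula, n per arm = [1.96·√(2·0.0525·0.9475) + 1.2816·√(0.07·0.93 + 0.035·0.965)]² / 0.035², which rounds up to 852. The total is 1704.
- Inflating for one Lan-DeMets O'Brien-Fleming efficacy look at 45% (factor 1.0019) gives 1707. Both are close to 1717, and power at 1717 is 90.2%.
- Total enrolment: 1717 / (0.80 × 0.75 × 0.95) = 3012, stated as about 3000.

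**4. Power of the mITT1 test alone**

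- mITT1 size = 1717 / 0.75 = 2289. This assumes the 25% late-onset share also applies among participants without mAb.
- If 7% versus 3.5% holds throughout mITT1, power is 96.4%.
- If participants with later onset get no benefit, the active-arm rate is 0.07 − 0.75 × 0.035 = 4.375%, and power is 77.4%.

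**5. Chance of a confirmatory mITT1 claim under each order**

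The protocol's order needs the primary and mITT1 tests both to be significant. The SAP's order needs the symptom test as well. Three correlated z-tests were simulated (500,000 draws), each at two-sided 5% and ignoring the interim look. The correlation between the mITT and mITT1 tests was √0.75. The correlation of the symptom test with the other two was set at 0 or 0.3.

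| Assumed symptom power | Protocol order | SAP order, correlation 0 | SAP order, correlation 0.3 |
|---|---|---|---|
| 5% (no effect) | 90% | 4.5% | 4.9% |
| 50% | 90% | 45% | 47% |
| 80% | 90% | 72% | 74% |
| 90% | 90% | 81% | 82% |
| 95% | 90% | 85% | 86% |

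The zero-correlation column can be checked by hand, for example 0.897 × 0.80 = 0.718. With no late-onset benefit the protocol's order gives about 76%, and the SAP's order gives 38%, 61%, 69% and 73% at symptom power 50%, 80%, 90% and 95% (correlation 0).

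**6. The other side of the trade**

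At 80% symptom power and correlation 0, the chance of the symptom claim is 71.7% in the protocol's order and 72.1% in the SAP's order. With no late-onset benefit the figures are 61.1% and 72.1%.

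**7. Type I error**

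Either order, fixed beforehand, holds the family at 5%. If the order is picked after the results, strong control is lost. Where the primary effect is real and both secondary nulls are true, leading with whichever test is positive gives up to 1 − 0.95² = 9.75% with independent tests. That case is narrow, because mITT makes up about three quarters of mITT1. The main costs are the blocked claim and a choice that cannot be shown to be blind.

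**The case against.** The strongest defence is the opening of Protocol section 9, which lets the SAP modify the protocol and requires an amendment only for major changes to the primary endpoint definitions or their analyses. Reordering secondary tests falls within that authority, so the SAP's order might simply govern and leave no choice to exploit. This fails because the SAP nowhere presents the reversal as intended and contradicts it in SAP 3.2, Appendix 1 and its own bullets. The SAP version history says the order was changed to match the protocol, which is evidence of intent only but points the same way.

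A second defence is that the sentence is leftover text and the intended order is plain. That is probably so. It is still the only explicit rule in the section on decision rules, and anyone following the SAP would apply it.

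A third is that the protocol never says the tests run in the listed order. Sequential testing, a numbered list and a named first key secondary endpoint leave no other reasonable reading.

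Some limits stand:

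- The primary mITT claim is tested before both endpoints and is safe under either order.
- The 96.4% is stand-alone power. The relevant figure is the joint 90%, which assumes that an effect planned for treatment within 3 days holds across mITT1.
- The SAP's order costs power for mITT1, not type I error, unless the order is chosen late.

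**Conclusion.** The concern holds. SAP 5.1 as written reverses the protocol's sequence and contradicts the rest of the SAP. Followed literally, it denies the mITT1 hospitalization/death claim whenever the symptom test fails. At an assumed 80% symptom power, the chance of that claim falls from about 90% to about 72–74%; with no symptom effect it falls to about 5%. These sizes rest on an assumed symptom power, assumed correlations of 0 to 0.3, and the planning effect holding across mITT1. The conflict itself rests on none of them. Because the sentence decides which confirmatory claims are allowed, it must be corrected before the sequence is applied.

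**What to change.** In SAP 5.1, replace the two gating sentences with text such as: *After a positive primary test, hospitalization/death through Day 28 in mITT1 is tested first. If that is positive, time to sustained alleviation is tested. If both are positive, the Hochberg family follows.* Number the two bullets 1 and 2 as in Protocol 9.1.

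Make the change before anyone who decides the order has seen unblinded secondary results. If that point has passed, record it as a correction to the order already pre-specified in the protocol.

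The cost is one short passage and two list numbers in the SAP, with no protocol amendment and no new data. A separate gap can be closed in the same edit: neither document says which analysis set carries the confirmatory alleviation test. Protocol 9.3.3 and SAP Appendix 1 assign it to mITT, mITT1 and mITT2.

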5.2. General Methods

All data will be presented by treatment group. Descriptive statistics will be provided for efficacy endpoints.

The number of participants screened, randomized to the double-blind treatment phase, completing the study drug administration, and completing the study will be summarized from the FAS. The reason for all discontinuations will be summarized by treatment group.

Baseline demographic and other characteristics will be tabulated for the FAS and summarized by treatment group. Quantitative variables will be described by standard descriptive statistics (mean, standard deviation, median and range), and qualitative variables will be summarized by frequency tables with number and proportion in each category (with the corresponding sample sizes).

5.2.1. Analyses for Binary Endpoints

For binary endpoints (ie, proportion of participants with COVID-19 related hospitalization or death from any cause through Day 28, proportion of participants with severe targeted signs/symptoms attributed to COVID-19 through Day 28, worsening status in 1 or more self reported COVID19 associated targeted signs/symptoms through Day 28 and proportion of participants with death (all-cause) through Week 24), proportion of participant with the event will be summarized for each group. Treatment comparison between the group will be

PFIZER CONFIDENTIAI	L
Page 19	

presented as the difference of proportions with its 95% confidence intervals using a similar analysis method as the primary endpoints.

5.2.2. Analyses for Continuous Endpoints

For continuous endpoint, (ie, viral titers measured via RT-PCR in nasal swabs over time), an ANCOVA model will be used to analyze change from baseline (Day 1) to Day 5. An MMRM analysis of covariance model will be used to analyze change from baseline over time. Estimated mean differences between treatments and their respective 95% CI and p-values will be calculated.

5.2.3. Analyses for Categorical Endpoints

For categorical endpoints (ie, proportion of participants with a resting peripheral oxygen saturation \geq 95% at Days 1 and 5), proportion of participants for each category will be summarized for each group and a test for homogeneity of odds ratio using Breslow-Day test will be summarized.

5.2.4. Analyes for Count Endpoints

For count endpoints (ie. number of COVID-19 related medical visits and number of hospitalizations/ICU visits), a negative binomial regression model analysis, using the log total number of days of data collection as the participant offset variable, will be conducted and the difference in estimated rate will be provided.

5.2.5. Analyses for Time-to-Event Endpoints

For time-to-event endpoints (ie, time (days) to sustained alleviation/resolution of all targeted signs/symptoms through Day 28 and duration of each targeted COVID-19 sign/symptom), 2 analyses may be provided: (1) a Cox proportional hazard regression model where the estimate of the hazard ratio for treatment (PF-07321332 vs Placebo), its confidence interval and p-value will be provided; and (2) Kaplan-Meier analysis where tabular summaries of the Kaplan-Meier curves providing the median and quartiles, will be provided for each treatment group. In addition, the KM curves will be presented graphically.

5.3. Methods to Manage Missing Data

For missing efficacy data other than time to event endpoints, a mixed baseline observation carried forward (BOCF)/ last observation carried forward (LOCF) approach will be used. See below:

• For efficacy endpoints related to COVID-19 targeted sign/symptoms, missing data at baseline will be treated as mild. If participant discontinues study due to AE or discontinues study at same time of treatment discontinuation due to lack of efficacy, missing data will use BOCF. Otherwise, missing data will use LOCF.

For safety data, missing and partial dates will be programmatically handled according to Pfizer standards.

PFIZER CONFIDENTIAL
Page 20

